
	
10. Adequate baseline pulmonary function test (FEV1 > 2 L or $\geq 75\%$ of predicted for height and age).
 
11. Because the teratogenicity of pembrolizumab and IL-2 is not known,
 
 Female subject of childbearing potential (WOCP) must not be pregnant confirmed by a negative urine or serum pregnancy test within 72 hours of the study registration. If the urine test cannot be confirmed as negative, a serum pregnancy test will be required. 
12. < 2 lines of prior therapy for metastatic melanoma. Cannot have received prior therapy with HD IL-2. May have had one prior line of therapy that included a check point inhibitor.
 
13. Not received radiation therapy within 21 days of initiation of study treatment, and the measurable disease must have been outside of the radiation port.
 
14. More than 3 weeks must have elapsed since any prior systemic therapy at the time the subject receives the first dose of pembrolizumab. Subject's toxicities must have recovered to a grade 1 or less (except for toxicities such as alopecia or vitiligo)
 
15. No second active malignancy.
 
16. No autoimmune diseases (see full eligibility criteria)
 
17. Willingness and ability to comply with scheduled visits, treatment plans, laboratory tests, and other study procedures.
 
18. Provide written informed consent and HIPAA authorization for release of personal health information, approved by an Institutional Review Board/Independent Ethics Committee (IRB/IEC). HIPAA authorization may be included in the informed consent or obtained separately.

STATISTICAL CONSIDERATIONS	
The optimal two-stage design to test the null hypothesis that $P \leq 0.260$ versus the alternative that $P \geq 0.500$ with 80% power and 0.05 level of significance proceeds as follows. After testing the drug on 11 patients in the first stage, the trial will be terminated if 3 or fewer respond. If the trial goes on to the second stage, a total of 29 patients will be studied. If the total number responding is less than or equal to 11, the drug is rejected. The probability of early termination at stage 1 with a total sample size of 11 is 0.685; the probability of going on to stage 2 with a total sample size of 29 is 0.315. The sample size calculation is conducted using the software PASS 13 (NCSS, Kaysville, Utah 2014)

TOTAL NUMBER OF SUBJECTS	N = Up to 29 subjects

[figure not shown]
ESTIMATED ENROLLMENT PERIOD	Estimated 36 months

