1. BACKGROUND AND RATIONALE

1.1 Disease Background

Metastatic melanoma continues to be a challenging disease to treat, with an estimated 9,940 expected deaths in the United States in 2015 [1]. The 5 year survival rate ranges between 5-19% [2] and the 10 year survival is less than 10% [3]. Patients with Stage IV melanoma continue to have a poor prognosis, with a mean survival of 8–10 months in large cohort analysis studies [4]. The National Comprehensive Cancer Network (NCCN) currently recommends the following therapies for treatment of advanced melanoma: 1) immunotherapy with anti-programmed cell death protein 1 (PD-1) monotherapy (Pembrolizumab or Nivolumab (NCCN category 1, which means it is based on high-level evidence, leading to NCCN consensus that the intervention is appropriate), 2) combination immunotherapy with Nivolumab/Ipilimumab, 3) targeted therapy if B-Raf proto-oncogene, serine/threonine kinase (BRAF)- mutated, 4) Dabrafenib/Trametinib (category 1 and preferred by NCCN), 5) Vemurafenib (category 1), 6) Dabrafenib (category 1) or 7) enrollment in a clinical trial. Although no longer recommended as a single agent for metastatic melanoma, Ipilimumab has been associated with long term survival in approximately 20% of patients [5]. The current recommended regimen of ipilimumab/nivolumab, has not provided mature data yet on overall survival (OS). Upon disease progression, a selected number of patients with Eastern Cooperative Oncology Group ECOG performance status (PS) 0-2 are offered the same agents (provided they did not have them before). In this setting (progression after initial treatment) High Dose interleukin-2 (HD IL-2) is one of the therapies recommended by NCCN. Despite these recent advances in increased options for treatment of advanced melanoma the prognosis remains poor for the majority of patients, and improved strategies to increase the number of patients benefited with longer and sustained responses are needed.

We propose to test two drugs in combination in order to determine if response rates can be improved over either agent as single therapy. The drugs which will be testing in combination are pembrolizumab and HD-IL-2. The next two sections will briefly describe the two drugs (their mechanism of action and some seminal clinical trials studies), and then we will conclude with providing the rationale for 1) combining the two drugs to test in this pilot study, and 2) the trial design and treatment sequencing we plan to use.

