1.2 Pembrolizumab: Immune Checkpoint Inhibitor

Interrupting the PD-1/programmed death-ligand 1 (PD-L1) interaction has emerged as an important weapon in immunotherapy [6]. Anti-PD-1 antibodies have been shown to induce positive radiological responses and improved survival rates in patients with melanoma. Sustained remissions remain low with average PFS still less than 6 months [7].

Pembrolizumab (formerly known as MK-3475) is a highly selective, humanized monoclonal IgG4-kappa isotype antibody against PD-1 that can disrupt the engagement of PD-1 with its ligands and impede inhibitory signals in T Cells, with resultant tumor recognition by cytotoxic T cells. The anti-tumor activity, side effects and safety of pembrolizumab in patients with melanoma was initially studied as part of the large, international, phase 1 KEYNOTE-001 trial.

In a pooled analysis of 411 patients with advanced melanoma enrolled in KEYNOTE-001, the response rate (RR) was 34% and was maintained in 81% of those patients, the median overall survival (OS) was 25.9 months [8] after a median follow-up duration of 18 months. The KEYNOTE-002 study of pembrolizumab versus chemotherapy confirmed the benefit of pembrolizumab in patients who had disease progression during or after ipilimumab therapy [9].

In this open-label, international expansion cohort of a phase 1 trial, patients (aged \geq 18 years) with advanced melanoma whose disease had progressed after at least two ipilimumab doses were randomly assigned to intravenous pembrolizumab at 2 mg/kg every 3 weeks or 10 mg/kg every 3 weeks until disease progression, intolerable toxicity, or consent withdrawal. A total of 173 patients received pembrolizumab 2 mg/kg (n=89) or 10 mg/kg (n=84). Median follow-up duration was 8 months. ORR was 26% at both doses (21 of 81 patients in the 2 mg/kg group and 20 of 76 in the 10 mg/kg group) (difference 0%, 95% CI -14 to 13; p=0.96). Treatment was well tolerated, with similar safety profiles in both groups and no drug-related deaths. The most common drug-related adverse events of any grade in the 2 mg/kg and 10 mg/kg groups were fatigue (29 [33%] vs 31 [37%]), pruritus (23 [26%] vs 16 [19%]), and rash (16 [18%] vs 15 [18%]). Grade 3 fatigue, reported in five (3%) patients in the 2 mg/kg pembrolizumab group, was the only drug-related grade 3 to 4 adverse event reported in more than one patient [8].

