3. ELIGIBILITY CRITERIA

3.1 Inclusion Criteria

Subject must meet all of the following applicable inclusion criteria to participate in this study:

1. Written informed consent and HIPAA authorization for release of personal health information prior to registration. **NOTE:** HIPAA authorization may be included in the informed consent or obtained separately.
2. Age \geq 18 years at the time of consent.
3. ECOG Performance Status of 0-1 within 28 days prior to registration (Appendix 1).
4. Life expectancy of 6 months or greater as determined by the site investigator.
5. Histologically-confirmed diagnosis of unresectable stage IV or metastatic melanoma not amenable to local therapy.
6. Measurable disease, defined as at least 1 tumor that fulfills the criteria for a target lesion according to RECIST 1.1 (Section 9), and obtained by imaging within 28 days prior to registration for protocol therapy.
7. Archival tissue (from the primary tumor or metastases) is mandatory if available for correlative studies. If archived tumor tissue is not available, the patient does not need to undergo a biopsy to obtain tissue and is still eligible for study.
8. < 2 lines of prior therapy for metastatic melanoma. Cannot have received prior therapy with HD IL-2. May have had one prior line of therapy that included a check point inhibitor.
9. Prior systemic cancer treatment must be completed at least 21 days prior to first dose of study drug and the subject must have recovered from all reversible acute toxic effects of the regimen (other than alopecia or vitiligo) to Grade \leq 1 or baseline.
10. Not received radiation therapy within 21 days of initiation of study treatment, and the measurable disease must have been outside of the radiation port.

11. Demonstrate adequate organ function as defined in the table below. All screening labs to be obtained within 28 days prior to registration.

System	Laboratory Value
Hematological	
White blood cell (WBC)	$\geq 3,000/\text{L}$
Absolute Neutrophil Count (ANC)	$\geq 1,000/\text{L}$ without the support of filgrastim
Hemoglobin (Hgb)	$\geq 9 \text{ g/dL}$
Platelet Count	$\geq 100 \times 10^9/\text{L}$
Renal	
Serum creatinine	$\leq 1.5 \text{ mg/dL}$
Calculated creatinine clearance ¹	$\geq 40 \text{ mL/min}$; for subjects with serum creatinine $> 1.5 \text{ mg/dL}$
Hepatic	
Total Bilirubin ² OR	$\leq 1.5 \times \text{ upper limit of normal (ULN)}$

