Direct Bilirubin	$\leq \text{ULN}$ for subjects with total bilirubin levels $> 1.5 \times \text{ULN}$
Aspartate aminotransferase (AST)	$\leq 2.5 \times \text{ULN}$ or $\leq 5 \times \text{ULN}$ for subjects with known hepatic metastasis
Alanine aminotransferase (ALT)	$\leq 2.5 \times \text{ULN}$ or $\leq 5 \times \text{ULN}$ for subjects with known hepatic metastasis
Coagulation	
International Normalized Ratio (INR) or	$\leq 1.5 \times \text{ULN}$; For subjects receiving warfarin or LMWH, the subjects must, in the site investigator's opinion, be clinically stable with no evidence of active bleeding while receiving anticoagulant therapy. The INR for these subjects may exceed $1.5 \times \text{ULN}$ if that is the goal of anticoagulant therapy.

1: Cockcroft-Gault formula will be used to calculate creatinine clearance (See SPM)

2: Except in patients with Gilbert's syndrome who must have a total bilirubin less than 3.0 mg/dL.

12. Adequate baseline pulmonary function test (PFT) (FEV1 $> 2 \text{ L}$ or $\geq 75\%$ of predicted for height and age).

13. Documented left ventricular ejection fraction (LVEF) of $> 45\%$, testing is required in patients with:

- Age ≥ 60 years old
- Clinically significant atrial and or ventricular arrhythmias including but not limited to: atrial fibrillation, ventricular tachycardia, second or third degree heart block
- History of coronary revascularization or ischemic symptoms

14. Females of childbearing potential must have a negative serum pregnancy test within 3 days prior to registration. **NOTE:** Females are considered of child bearing potential unless they are surgically sterile (have undergone a hysterectomy, bilateral tubal ligation, or bilateral oophorectomy) or they are naturally postmenopausal for at least 12 consecutive months.

15. Females of childbearing potential and males must be willing to abstain from heterosexual activity or to use 2 forms of effective methods of contraception from the time of informed consent until 120 days after treatment discontinuation. The two contraception methods can be comprised of two barrier methods, or a barrier method plus a hormonal method.

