3.2 Exclusion Criteria

Subjects meeting any of the criteria below may not participate in the study:

1. Active infection requiring systemic therapy
2. Pregnant or breastfeeding. **NOTE:** breast milk cannot be stored for future use while the mother is being treated on study.
3. Known additional malignancy that is active and/or progressive requiring treatment; exceptions include basal cell or squamous cell skin cancer, in situ cervical or bladder cancer, or other cancer for which the subject has been disease-free for at least five years.
4. Active central nervous system (CNS) metastases. **NOTE:** if prior metastasis but treated and clinically stable for 1 month after treatment are eligible. Subjects with 3 or fewer brain metastases that are less than 1 cm in diameter and asymptomatic are eligible.
5. Surgery within 4 weeks prior to study treatment except for minor procedures. **NOTE:** Hepatic biliary stent placement is allowed.
6. Uncontrolled or poorly-controlled hypertension (> 160 mmHg systolic or > 100 mmHg diastolic for > 4 weeks) despite standard medical management.
7. Serious or non-healing wound, ulcer, or bone fracture within 28 days prior to initiation of study treatment.
8. Any Grade 3-4 GI bleeding within 3 months prior to initiation of study treatment.

9. History of deep vein thrombosis, pulmonary embolism, or any other significant thromboembolism (venous port or catheter thrombosis or superficial venous thrombosis are not considered “significant”) during the 3 months prior to initiation of study treatment.
10. Any arterial thromboembolic events, including but not limited to myocardial infarction, transient ischemic attack, cerebrovascular accident, or unstable angina, within 6 months prior to initiation of study treatment.
11. Gross hemoptysis within 2 months of initiation of study treatment.
12. Has any condition that, in the opinion of the investigator, might jeopardize the safety of the patient or interfere with protocol compliance.
13. Has any mental or medical condition that prevents the patient from giving informed consent or participating in the trial.
14. Known hypersensitivity to pembrolizumab or IL-2 or any of their components.
15. Known history of active tuberculosis.
16. Concurrent systemic steroid therapy with doses above physiologic level.

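### No printed criterion specifically names a past, recovered immune-related pneumonitis, myocarditis or encephalitis on earlier anti-PD-1/PD-L1 therapy, although Table 2 allows no return to pembrolizumab after these events

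*Combined protocol and SAP*

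**What the plan says.** Entry. Section 3.1, item 8 permits fewer than two prior lines for metastatic disease and adds: "May have had one prior line of therapy that included a check point inhibitor". The class of inhibitor is not restricted. Section 1.1 lists "immunotherapy with anti-programmed cell death protein 1 (PD-1) monotherapy" and nivolumab/ipilimumab among the recommended treatments, so the prior line can contain an anti-PD-1 agent.

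Recovery. Item 9 requires 21 days since prior systemic therapy and that "the subject must have recovered from all reversible acute toxic effects of the regimen", to Grade 1 or less or to baseline. Synopsis item 14 is similar: "toxicities must have recovered to a grade 1 or less". Neither limits the type or worst past grade of an event.

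On study. Table 2 in section 6.1.3 sets the action on pembrolizumab by event and grade. Some events lead to withholding, others to permanent discontinuation.

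Other screens. Exclusion 12 bars a subject who "Has any condition that, in the opinion of the investigator, might jeopardize the safety of the patient or interfere with protocol compliance". Exclusion 16 bars concurrent steroids above physiologic dose. Exclusion 17 bars a history of autoimmune disease through an open-ended list and refers to the Study Procedures Manual (SPM) for detail. Section 10.2.6 calls for a clinical evaluation to exclude subjects with contraindications to Proleukin and those with significant organ impairment.

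**The concern.** The entry rule looks at present status, whereas for certain events Table 2 looks at what has happened. If Grade 3 myocarditis occurred on study pembrolizumab, the drug would be stopped for good, even after full recovery. If the same event occurred on an earlier anti-PD-1 and resolved, inclusions 8 and 9 would be met and the subject could receive pembrolizumab again.

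That subject would then go on to HD IL-2. Section 10.2.6 reports hypotension in 71% and dyspnea in 43% of 525 patients treated with Proleukin and says that adverse events are sometimes fatal. At stake is the safety of a small number of people, and whether all sites handle them the same way.

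**Working it through.** **1. Which events have no route back in Table 2**

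| Event | Action on pembrolizumab | Return possible? |
|---|---|---|
| Colitis, Grade 2-3 | Withhold | Yes, at Grade 1 or baseline (6.1.1) |
| Endocrinopathy, Grade 3-4, where withheld | Withhold | Yes, at Grade 2 or less and controlled (Table 2 note) |
| Pneumonitis, Grade 3-4 or recurrent Grade 2 | Permanent stop | No |
| Myocarditis, Grade 3-4 | Permanent stop | No |
| Encephalitis, Grade 3 (named) or Grade 4 | Permanent stop | No |

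**2. Whether a printed criterion reaches a recovered case of the last three**

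- Inclusions 8 and 9: met after washout and recovery.
- Exclusion 12: can be invoked, but it rests on investigator opinion and is phrased in the present tense.
- Exclusion 14: hypersensitivity only.
- Exclusion 16: no longer applies once steroids are at or below physiologic dose.
- Exclusion 17: prints 13 conditions, and none is pneumonitis, myocarditis or encephalitis. It does name Guillain-Barré syndrome, and arguably reaches colitis, hepatic and renal events through inflammatory bowel disease, autoimmune hepatitis and glomerulonephritis.
- Lung function testing and screening chest CT: done in all, but they show current status.
- LVEF: testing is required only at age 60 or over, with significant arrhythmia, or with "History of coronary revascularization or ischemic symptoms". A younger subject with recovered myocarditis and none of these need not be tested.
- Calendar footnote 1: prior treatments are documented, but immune-related events on them are not mentioned.

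**3. How many subjects**

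The documents give no rate for these events and no count of subjects with prior anti-PD-1. The only guide is the 173-patient ipilimumab-refractory pembrolizumab cohort in section 1.2, where Grade 3 fatigue "was the only drug-related grade 3 to 4 adverse event reported in more than one patient".

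- Denominator check: the text prints five patients (3%). 5/173 = 2.9% fits; 5/89 = 5.6% does not. I therefore read the sentence across both dose groups.
- Each other Grade 3-4 type: at most 1/173 = 0.58% observed; exact (Clopper-Pearson) two-sided 95% upper limit 3.18%.
- Three types together: at most 3/173 = 1.73% observed; upper limit 4.98%.

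Expected subjects = number with prior anti-PD-1 monotherapy × rate. The numbers 7, 15 and 29 are illustrative: about a quarter, about a half, and all of 29.

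| Prior anti-PD-1 monotherapy | One type, 1/173 | One type, upper limit | Three types, 3/173 |
|---|---|---|---|
| 7 | 0.04 | 0.22 | 0.12 |
| 15 | 0.09 | 0.48 | 0.26 |
| 29 | 0.17 | 0.92 | 0.50 |

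For the three types together at the upper limit, 29 × 0.0498 is about 1.45.

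**4. Design figures**

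The two-stage rule in section 12.3 (3/11, then 11/29) reproduces: early-termination probability 0.6854 against the stated 0.685, exact type I error 0.0429, power 0.8075. These depend only on the cut-offs, sample sizes and hypothesised rates, so an added exclusion leaves them unchanged.

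**The case against.** The strongest reply is that the plan already has enough cover. Exclusion 17 is based on history, so recovery does not cure it; it is open-ended and points to an SPM list that is not available here. Exclusion 12 is made for this kind of judgement, and footnote 1 ensures that the investigator knows which agent was given before. Section 10.2.6 adds a screen for Proleukin contraindications. This stands in part. A reader might infer that nothing in the protocol covers these subjects, and the documents do not support that. They support the narrower statement that no printed criterion specifically names the events, so the outcome depends on discretion, on how exclusion 17 is read, or on a list outside the protocol.

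A second reply is that Table 2 governs study pembrolizumab during an on-study event. Stopping a drug in acute toxicity and rechallenging a recovered patient after washout are different decisions. This also stands. A reader might infer that the protocol contradicts itself; it does not, because it never applies Table 2 to entry. The alignment is an inference on safety grounds. In addition, the general-instructions row of Table 2 is blank in the text available, so the routes back are read from section 6.1.1 and the table note.

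Third, one might want to bar every event that Table 2 stops permanently. That would add Grade 3-4 hepatic and renal events, Grade 4 colitis and any other Grade 4 or recurrent Grade 3 event. Exclusion 17 arguably reaches some of these already, and the estimate above does not count them, so a bar that wide could not be called low-cost on these figures.

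**Conclusion.** The point holds as a cheap safety improvement. On the printed text, a subject with a past, recovered Grade 3-4 or recurrent Grade 2 pneumonitis, Grade 3-4 myocarditis or Grade 3-4 encephalitis on anti-PD-1/PD-L1 therapy can meet inclusions 8 and 9. Entry is then prevented only if exclusion 12 is invoked, exclusion 17 or its SPM list is read to include the event, or the evaluation in section 10.2.6 finds a contraindication to Proleukin.

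The size is small: about 0.12 to 0.50 expected subjects, or up to about 1.45 of 29 at the upper limit. This assumes that the section 1.2 cohort is a fair guide and that 7 to 29 subjects had prior anti-PD-1 monotherapy. It does not cover recurrent Grade 2 pneumonitis or events after nivolumab/ipilimumab, for which the documents give no rates. The 0.50 is a point estimate from an observed maximum, not a ceiling. A reader might infer a threat to the response-rate test; nothing in the documents supports one.

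**What to change.** Add to section 3.2 and mirror in synopsis item 12: *Prior anti-PD-1/PD-L1-containing therapy complicated by Grade 3-4 or recurrent Grade 2 pneumonitis, Grade 3-4 myocarditis, or Grade 3-4 encephalitis considered immune-related.* Leave exclusion 17 and its exemptions unchanged. Extend calendar footnote 1 to record immune-related events on prior checkpoint inhibitors and their worst grade. If the SPM list already names the three events, print them in the protocol.

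The cost is one exclusion line, one synopsis line and one medical-history field, with no new test or visit. Sites already review toxicity from the prior regimen under inclusion 9. The downside is the loss of a few subjects who might be safely rechallenged, including some whose event on nivolumab/ipilimumab may have been due to ipilimumab. After monotherapy, the accrual loss is of the size given above; after the combination it cannot be derived from the documents.

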3.2 Exclusion Criteria

Subjects meeting any of the criteria below may not participate in the study:

1. Active infection requiring systemic therapy
2. Pregnant or breastfeeding. **NOTE:** breast milk cannot be stored for future use while the mother is being treated on study.
3. Known additional malignancy that is active and/or progressive requiring treatment; exceptions include basal cell or squamous cell skin cancer, in situ cervical or bladder cancer, or other cancer for which the subject has been disease-free for at least five years.
4. Active central nervous system (CNS) metastases. **NOTE:** if prior metastasis but treated and clinically stable for 1 month after treatment are eligible. Subjects with 3 or fewer brain metastases that are less than 1 cm in diameter and asymptomatic are eligible.
5. Surgery within 4 weeks prior to study treatment except for minor procedures. **NOTE:** Hepatic biliary stent placement is allowed.
6. Uncontrolled or poorly-controlled hypertension (> 160 mmHg systolic or > 100 mmHg diastolic for > 4 weeks) despite standard medical management.
7. Serious or non-healing wound, ulcer, or bone fracture within 28 days prior to initiation of study treatment.
8. Any Grade 3-4 GI bleeding within 3 months prior to initiation of study treatment.

9. History of deep vein thrombosis, pulmonary embolism, or any other significant thromboembolism (venous port or catheter thrombosis or superficial venous thrombosis are not considered “significant”) during the 3 months prior to initiation of study treatment.
10. Any arterial thromboembolic events, including but not limited to myocardial infarction, transient ischemic attack, cerebrovascular accident, or unstable angina, within 6 months prior to initiation of study treatment.
11. Gross hemoptysis within 2 months of initiation of study treatment.
12. Has any condition that, in the opinion of the investigator, might jeopardize the safety of the patient or interfere with protocol compliance.
13. Has any mental or medical condition that prevents the patient from giving informed consent or participating in the trial.
14. Known hypersensitivity to pembrolizumab or IL-2 or any of their components.
15. Known history of active tuberculosis.
16. Concurrent systemic steroid therapy with doses above physiologic level.
17. History of autoimmune disease, including but not limited to myasthenia gravis, myositis, autoimmune hepatitis, systemic lupus erythematosus, rheumatoid arthritis, inflammatory bowel disease, vascular thrombosis associated with anti-phospholipid syndrome, granulomatosis with polyangiitis, Sjögren’s syndrome, Guillain-Barré syndrome, multiple sclerosis, vasculitis, or glomerulonephritis. See Study Procedures Manual (SPM) for a detailed list.
 - Subjects with a history of autoimmune-related hypothyroidism on a stable dose of thyroid replacement hormone may be eligible for this study.
 - Subjects with controlled Type I diabetes mellitus on a stable dose of insulin regimen may be eligible for this study.
 - Subjects with a history of celiac disease may be eligible if controlled with diet.
18. Treatment with any investigational agent within 21 days prior to initiation of study treatment and the subject must have recovered from the acute toxic effects of the regimen.
19. Prior organ transplant including allogeneic transplantation.

